15 APPENDICES

Not applicable.

CRO	Contract Research Organization
CSR	Clinical Study Report
DD	Drug Dictionary (WHO Coding Thesaurus)
DBR	Database Review
DMP	Data Management Plan
DVP	Data Validation Plan
ED	Exposure Day
EDC	Electronic Data Capture
EOT	End of Trial
eCRF	Electronic Case Report Form
FAS	Full Analysis Set
FVIII	Coagulation Factor VIII
FVIII:C	Factor VIII-coagulant

STATISTICAL ANALYSIS PLAN

Protocol No: WIL-27

Version Number: 5.0

Date of Issue: 2018-05-08

Page 8 of 27

Abbreviation	Description
HJHS	Hemophilia Joint Health Score
ICF	Informed Consent Form
ID	Identifier
IMP	Investigational Medicinal Product
IRB	Institutional Review Board
ITT	Intention-To-Treat
IU	International Unit
IV	Intravenous
IVR	Incremental in Vivo Recovery
LOCF	Last Observation Carried Forward
MedDRA	Medical Dictionary for Regulatory Activities
MRT	Mean Residence Time
N	Number of Subjects/Observations
OS	One-stage assay
PK	Pharmacokinetic
POP	Postoperative
PP	Per-Protocol
PT	Preferred Term
PTP	Previously Treated Subject
QC	Quality Control
SAE	Serious Adverse Event
SAF	Safety Analysis Set
SAP	Statistical Analysis Plan
SAS	Statistical Analysis Software package
SD	Standard Deviation
SOC	System Organ Class
SOP	Standard Operating Procedure
SABR	Spontaneous Annualized Bleeding Rate
SURG	Surgery analysis set

STATISTICAL ANALYSIS PLAN**Protocol No: WIL-27**

Version Number: 5.0

Date of Issue: 2018-05-08

Page 9 of 27

Abbreviation	Description
T _{1/2}	In Vivo Half-Life
TABR	Total Annualized Bleeding Rate
TEAE	Treatment Emergent Adverse Event
TLFs	Tables, Listings, Figures
T _{max}	Time to Reach Maximum Plasma Concentration
TS	Trial Statistician
Vd	Volume of distribution
VWD	Von Willebrand Disease
VWF	Von Willebrand Factor
VWF:Ac	VWF activity
VWF:Ag	Von Willebrand Factor Antigen
WHO	World Health Organization

STATISTICAL ANALYSIS PLAN Protocol No: WIL-27	
Version Number: 5.0	Page 10 of 27
Date of Issue: 2018-05-08	

1 STUDY MATERIAL

The following material was considered for this SAP:

Document	Version, Date
Protocol, incl. last amendment	2017-09-07, including Amendments #1 (2016-11-14), #2 (2017-01-16), #04 (2017-09-07)
CRF	TBD
DMP	TBD
DVP	TBD

2 STUDY INFORMATION

2.1 Primary objective

The primary objective of this study is to determine the efficacy of *Wilate* in the prophylactic treatment of previously treated subjects (PTP) with severe hemophilia A.

2.2 Secondary objective

The secondary objectives of this study are to:

- Determine the efficacy of *Wilate* in the treatment of breakthrough bleeding episodes (BEs)
- Calculate the FVIII:C pharmacokinetics (PK) for *Wilate* at baseline and after 6 months of prophylactic treatment
- Calculate the FVIII:C incremental IVR of *Wilate* over time (at baseline, and at 3 and 6 months of treatment)
- Assess the association between AB0 blood type and the FVIII:C half-life of *Wilate*
- Assess the association between the VWF:Ag concentration and the FVIII:C half-life of *Wilate*
- Assess the safety and tolerability of *Wilate*
- Assess the immunogenicity of *Wilate*

2.3 Additional Objective:

An additional objective of this study is the descriptive efficacy of *Wilate* in surgical prophylaxis.

STATISTICAL ANALYSIS PLAN	
Protocol No: WIL-27	
Version Number: 5.0	Page 11 of 27
Date of Issue: 2018-05-08	

2.4 Study design

This study is designed as a prospective, international, multi-center phase 3 study. Further details are given in the overview below:

FLOW CHART FOR PK ASSESSMENT AND PROPHYLACTIC TREATMENT

Part I

	Screening Visit	PK Patients	Non-PK Patients	Day-14 Visit (14-21 days)	Day-30 Visit (±3 days)	3-Month Visit (±2 weeks)
		PK Visit	Non-PK Visit			
Informed consent	x					
Inclusion and exclusion criteria	x					
Demographics	x					
Weight	x	x [1]	x [1]			x [1]
Height	x					
Medical history (incl. FVIII treatment 6 months before screening)	x					
Vital signs	x	x [2]	x [4]			x [4]
Physical examination	x					
Routine safety laboratory	x	x [3]	x [4]			x [1]
Determination of CD4+ levels [8]	x					
Determination of AB0 blood group [9]	x					
HJHS, unless obtained within 3 months before screening	x					
PK injection (50 ± 5 IU/kg)		x				
Blood sampling for FVIII:C (OS and CHR) for PK assessment		x [5]				
IVR injection			x [10]			x
Blood sampling for FVIII:C IVR (OS and CHR)			x [6]			x [6]
Factor VIII inhibitor [11]	x	x [1]	x [1]	x [1]	x [1]	x [1]
VWF:Ag and VWF:Ac		x [6]	x [6]	x [1]	x [1]	x [6]
Parvovirus B19 antibodies		x [1]	x [1]			
Retention sample for possible virus marker testing		x [1]	x [1]			
Patient diary review				x	x	x
Adverse event monitoring		x	x	»	»	»
Concomitant medications	x	»	»	»	»	»

PK = pharmacokinetic, IVR = in vivo recovery, HJHS = Hemophilia Joint Health Score, OS = one-stage assay, CHR = chromogenic assay, VWF:Ag = von Willebrand factor antigen, VWF:Ac = VWF activity

<h2 style="margin: 0;">STATISTICAL ANALYSIS PLAN</h2> <h3 style="margin: 0;">Protocol No: WIL-27</h3>	
Version Number: 5.0 Date of Issue: 2018-05-08	Page 12 of 27

Part II

	PK Patients	Non-PK Patients	
	PK Study Completion Visit at 6 months (+2 weeks)	Non-PK Study Completion Visit at 6 months (+2 weeks)	Follow-up Contact 30 days (±3 days) after Study Completion Visit
Informed consent			
Inclusion and exclusion criteria			
Demographics			
Weight	x [1]	x [1]	
Height			
Medical history (incl. FVIII treatment 6 months before screening)			
Vital signs	x [2]	x [4]	
Physical examination	x	x	
Routine safety laboratory	x [3]	x [4]	
Determination of CD4+ levels [8]			
Determination of AB0 blood group [9]			
HJHS, unless obtained within 3 months before screening			
PK injection (50 ± 5 IU/kg)	x		
Blood sampling for FVIII:C (OS and CHR) for PK assessment	x [5]		
IVR injection		x	
Blood sampling for FVIII:C IVR (OS and CHR)		x [6]	
Factor VIII inhibitor [11]	x [1]	x [1]	
VWF:Ag and VWF:Ac	x [6]	x [6]	
Parvovirus B19 antibodies	x [7]	x [7]	
Retention sample for possible virus marker testing			
Patient diary review	x	x	
Adverse event monitoring	x	x	x [12]
Concomitant medications	x	x	

- [1] Before injection
- [2] Before injection as well as 1 h (±5 min) and 48±2 h after injection
- [3] Before injection as well as 48±2 h after injection **[local laboratory]**
- [4] Before injection as well as 15±5 min after injection
- [5] Blood sampling within 1 h before injection and 15±5 min, 1 h (±5 min), 3 h (±15 min), 6 h (±30 min), 9±1 h, 24±2 h, 30±2 h, and 48±2 h after end of injection **[central laboratory]**
- [6] Blood sampling within 1 h before injection as well as 15±5 min after the end of injection **[central laboratory]**
- [7] If first sample was negative for parvovirus B19 antibodies (sample to be taken before injection) **[central laboratory]**
- [8] CD4+ count to be repeated if interval between Screening Visit and first injection exceeds 30 days. To be included into the study, the patient's CD4+ count must be >200/μL (i.e., inclusion criterion no. 4).
- [9] Unless obtainable from patient's medical history
- [10] First prophylactic injection
- [11] Blood sampling for inhibitor testing should preferably be done at the time of trough FVIII:C levels **[central laboratory]**
In case of positive inhibitor results, inhibitor retesting using a second, separately drawn sample should be performed, preferably within 15 days of becoming aware of the positive result.
- [12] Documentation of AEs potentially related to thromboembolic events only

<h2 style="margin: 0;">STATISTICAL ANALYSIS PLAN</h2> 
Protocol No: WIL-27
	
Version Number: 5.0 Date of Issue: 2018-05-08	Page 13 of 27

FLOW CHART OF ASSESSMENTS FOR SURGICAL PROPHYLAXIS

	Within 12 hours before start	Within 3 hours before start	Surgery		POP day 1	Any POP day	End of POP period [1]	3-8 weeks after surgery	
			Intra-operatively	End					
Body weight	x								
Type of surgery	x								
Location of surgery	x								
Severity of surgery	x								
Expected duration of surgery	x								
Expected average/ maximum blood loss during surgery	x								
Actual duration of surgery				x					
Actual blood loss during surgery				x					
Administration of IMP		x	(x)	(x)	(x)	(x)	(x)		
FVIII plasma levels		#	(#)	(#)	# [2]	#	#		
VWF:Ag and VWF:Ac		#			# [2]	#	#		
Presence of wound hematomas					x	x	x		
Routine safety laboratory	x				(x)	(x)	(x)		
Vital signs	x		x		x				
Efficacy assessment				S			H		
Overall efficacy assessment							I		
FVIII inhibitor								x	
Narrative of outcome							x		
Concomitant medications	throughout observation period								
Adverse event monitoring	throughout observation period								

POP, postoperative, VWF:Ag = von Willebrand factor antigen, VWF:Ac = VWF activity

() Optional

Samples to be taken immediately before (≤ 30 min) and 30 ± 15 min after IMP administration

[1] Time immediately after the last surgical suture

[2] For major surgery, mandatory for the first 3 postoperative doses

S, performed by surgeon; H, performed by hematologist; I performed by Investigator

2.5 Planned sample size

55 male subjects with severe hemophilia A ($<1\%$ FVIII:C) aged ≥ 12 years with at least 150 previous exposure days (EDs) to a FVIII concentrate will be enrolled to obtain evaluable data on 50 subjects who complete 6 months of prophylactic treatment. Of these 50 subjects, 20 subjects will undergo two 2-day PK Assessment Phases of 1 dose of $50 \text{ IU} \pm 5 \text{ IU Wilate/kg}$ body weight (BW) before the start and after the end of the Prophylactic Treatment Phase. Of the 20 patients undergoing the PK assessment, a minimum of 4 patients should be between ≥ 12 and <17 years of age.

No statistical sample size estimation was performed. The chosen sample size of 50 evaluable subjects will, however, be sufficient to reject the null hypothesis of a mean TABR >29 with

STATISTICAL ANALYSIS PLAN Protocol No: WIL-27
	
Version Number: 5.0	Page 14 of 27
Date of Issue: 2018-05-08	

a power of >90% if the mean TABR is not greater than 20 BEs per person year with a maximum standard deviation of 15.

3 GENERAL INFORMATION

3.1 Background details

The data will be transferred to SAS from the Clinical Data Management System OPVERDI via a validated procedure. If applicable external data will also be transferred to SAS for presentation of these data in the statistical analyses.

3.2 Deviations from the trial protocol with regard to statistical analyses

No deviations from the protocol are planned.

3.3 Individual protocol deviations

Any deviation from protocol will be discussed case by case before database lock whether the deviation has to be regarded as minor or as major (and therefore will lead to exclusion from particular analysis populations).

Examples for minor protocol violations may be deviations from scheduled investigation time.

Criteria for major protocol violations will at least include:

- Any substantial violation of in- or exclusion criteria.
- Use of concomitant medication that may interfere with the assessment of efficacy.

The final decision about the classification of individual protocol deviations and their consequences regarding assignment of subjects to analysis sets will be made during the data review meeting (DBR). A complete listing of protocol deviations and the judgment for assessment of subject disposition will be approved by the Sponsor and signed before database lock. All deviations along with the disposition of each subject will be recorded in a separate database member that will become part of the study database. A description of all major protocol violations will be included in the table part of the CSR.

4 ANALYSIS POPULATIONS

The disposition of subjects will be displayed according to the following analysis populations:

- Safety (SAF) population
- Full Analysis Set (FAS)
- Per-Protocol (PP) population
- Pharmacokinetic (PK) set

STATISTICAL ANALYSIS PLAN Protocol No: WIL-27
	
Version Number: 5.0	Page 15 of 27
Date of Issue: 2018-05-08	

- Surgery (SURG) set

4.1 Safety population

The **safety (SAF) set** will include all subjects who received at least one infusion of IMP.

4.2 Full analysis set population

The **full analysis set (FAS)** defined according to the intention-to-treat (ITT) principle will include all enrolled subjects who received at least one infusion of IMP after the initial PK or at Non-PK Visit.

4.3 Per-protocol population

The **per-protocol (PP) set**, i.e. a subset of the FAS, will exclude subjects with major protocol deviations which may have an impact on the evaluation of the primary study outcome parameter (major protocol deviations as defined during DBR).

4.4 Pharmacokinetic population

The **pharmacokinetic (PK) set** will include all subjects for which at least one valid *Wilate* PK profile has been obtained.

4.5 Surgery population

The **surgery (SURG) set** will be a subset of the FAS, containing all subjects who underwent a surgical procedure treated with *Wilate* during their Prophylactic Treatment Phase

4.6 Subgroup analyses

The analyses of the efficacy endpoints ‘efficacy of prophylactic treatment’ and ‘efficacy in treatment of breakthrough BEs’ will be presented for the following subgroups:

- Age (‘<16 years’ and ‘≥16 years’)
- Race (‘American Indian or Alaska Native,’ ‘Asian,’ ‘Black or African American,’ ‘Native Hawaiian or Other Pacific Islander,’ ‘White,’ ‘Other’);
- Geographical region (‘patients in the US,’ ‘patients outside the US’);

Analysis of PK parameters will be presented by age (‘< 16 years’ and ‘≥16 years’).

5 STATISTICAL ANALYSES

All statistical analyses will be performed using SAS® for Windows (Version 9.3 or later).

Descriptive statistics will always be given for the entire population.

The analysis of safety will be based on the SAF set.

The evaluation of the primary endpoint will be performed on the FAS (ITT analysis) and on the PP set (PP analysis).

STATISTICAL ANALYSIS PLAN Protocol No: WIL-27
	
Version Number: 5.0	Page 16 of 27
Date of Issue: 2018-05-08	

For secondary endpoints, ITT and PP analyses will be carried out, unless these analysis sets differ by no more than 5% of subjects in the FAS.

Analysis of the PK properties of *Wilate* will be based on the PK set.

Analysis of the efficacy and safety of *Wilate* in surgeries will be based on the SURG set.

If not stated otherwise the following standard descriptive statistics will be presented:

Descriptive statistics for continuous data

Number of subjects (N), arithmetic mean, standard deviation (SD), minimum, lower quartile, median, upper quartile and maximum will be presented. Usually mean and quartiles will have 1 decimal more, SD 2 decimals more than the original values (as given with min, max); N has no decimals. These descriptive statistics will be determined for measured values and for differences to baseline.

Descriptive statistics for categorical data

Absolute frequencies (N) will be presented with 0, relative frequencies (%) with 1 or 2 decimals, as applicable. For changes from baseline, shift tables may be generated.

Inferential statistics

If not stated otherwise all statistical tests will be performed as described in the corresponding sections below.

All p-values will be rounded to 4 decimals (p<0.0001 will be displayed, if the p-values are less than 0.0001). Statistical significance will be declared if the rounded p-value will be less than 0.050.

All confidence intervals (CI) will be derived two-sided and at a confidence probability of $1 - \alpha = 0.95$.

Listings

All subject data will be listed by subject. Identification variable will be the subject ID (composed of study, center and subject number separated by a hyphen, e.g. '27-01-01'). Any derived data listed will also be stored permanently and will be calculated as outlined in section 8.1 of this SAP.

5.1 Conventions

5.1.1 Baseline definition

Assessments at screening visit or the first IVR measurement (at PK or Non-PK visit, respectively) are considered as baseline.

STATISTICAL ANALYSIS PLAN Protocol No: WIL-27
	
Version Number: 5.0	Page 17 of 27
Date of Issue: 2018-05-08	

5.1.2 Missing data

In case of missing weight documentation data will be imputed using the Last Observation Carried Forward (LOCF) approach to calculate the dose per kg body weight (IU/kg).

In case of missing date/time documentations for PK or IVR samplings the corresponding scheduled time point will be used for analysis.

No further imputations for missing data will be performed.

Calculations pertaining to the derivation of annual bleeding rates will be based on documented time periods only.

5.1.3 Pooling of centers

All tables will be presented in total over all participating countries and centers. The distribution of number of subjects per country will be presented in the disposition section of the report.

5.2 Demographic and other background data

5.2.1 Basic description

The disposition of subjects (cf. Section 4) will be tabulated for the entire population. Details on protocol deviations will be listed.

Discontinued subjects will be described by frequency distributions including the reasons and in individual listings.

Demographic data (age, weight, height, BMI, race, ethnic group) will be summarized in tables and presented for the SAF and FAS population. Other baseline or background data, e.g. disease-specific information, will comprise descriptive tables for the SAF and FAS population for the following variables:

- Blood group
- VWF:Ag, VWF:Ac and CD4+ levels at baseline
- FVIII inhibitor level
- Vital Signs (Systolic and diastolic blood pressure, pulse and body temperature) at screening
- Physical examination (normal/abnormal)
- Hemophilia joint health score (HJHS)
- Results of Parvovirus B19 antibodies
- Previous annual bleeding rate (ABR) calculated from number of bleeding episodes during the past 6 months documented under Medical history

The following background data will only be listed:

- Medical history (including FVIII treatment during the last 6 months before screening)

STATISTICAL ANALYSIS PLAN Protocol No: WIL-27
	
Version Number: 5.0	Page 18 of 27
Date of Issue: 2018-05-08	

- Concomitant Medication

5.3 IMP exposure, compliance

Treatment will be administered prophylactically as defined in the protocol. Each treatment will be recorded in the diary along with the reason for treatment (prophylaxis, bleeding, prevention of recurrent bleeding, prophylaxis after surgery or other reason) and transferred to the CRF. Treatments in context of IVR measurements and surgeries will be documented in the eCRF only.

All IMP treatment details will be listed.

5.4 Medical history

Data on medical history will be listed. Medical history will be coded according to the Medical Dictionary for Regulatory Activities (MedDRA). Codes will be reviewed by a Medical Expert and approved by the sponsor before data base lock.

5.5 Concomitant medication

Any relevant medication taken at time of screening and all new medications taken by the subject during the study period are defined as ‘Concomitant’. Any changes of medications during the study period will also be recorded.

All details of concomitant medications will be listed including, the route, dose, frequency, start and stop date and indication.

Medications will be coded using the WHO DD thesaurus in the version current at the time of database lock. Coding will be performed by the CRO and agreed upon with the sponsor before data base lock. (cf. DMP). For concomitant medications tables will show the frequencies of subjects by WHO DD preferred term. Prior medication will only be listed.

5.6 Concomitant non-pharmacological measures, pre-medication

Not applicable.

5.7 Efficacy

The analysis of the efficacy of prophylactic treatment with *Wilate* will be based on the FAS and the PP set.

Primarily, all obtained data on treatment characteristics (IMP dosages, frequencies, total consumption) and BEs (duration, frequency, efficacy assessment) will be described by providing summary statistics.

STATISTICAL ANALYSIS PLAN Protocol No: WIL-27	
Version Number: 5.0	Page 19 of 27
Date of Issue: 2018-05-08	

5.7.1 Primary endpoint

The primary endpoint of this study is a 50% reduction of the total annualized bleeding rate (TABR) observed in the GENA-01 study with a total of 58.1 BEs per subject per year.

The efficacy of prophylactic treatment with *Wilate* will be statistically evaluated by comparing the primary endpoint, i.e., TABR under prophylaxis, with a predefined threshold of 29 per subject per year. This threshold corresponds to 50% of the TABR reported in GENA-01, a study in which previously treated adolescent and adult subjects with severe hemophilia A received on-demand FVIII treatment only.

TABR will be calculated as the total number of BEs in the time period between first dose of IMP and the Study Completion Visit, divided by the duration (in years) between first dose of IMP and the Study Completion Visit. Surgery periods, and BEs occurring within these periods, will be excluded from the calculation of TABR.

A confirmative one-sided, one-sample Poisson-test will be used to test whether the mean TABR in subjects treated prophylactically with *Wilate* is below the threshold of 29 BEs per subject year ($\alpha = 2.5\%$). A corresponding two-sided 95% CI for the TABR will also be provided.

If μ denotes the mean TABR, then the following pair of hypotheses will be tested:

$$H_0: \mu \geq 29 \text{ vs. } H_1: \mu < 29$$

The null hypothesis will be rejected (at a one-sided alpha level of 2.5%) if the upper limit of the one-sided 97.5% confidence interval for μ is strictly less than 29.

This mentioned confidence interval will be derived from a generalized linear model with a Poisson error, log-link function and log (exposure time) as offset term.

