9.1 Determination of Sample Size

The sample size of 55 patients to be enrolled was based on medical and regulatory reasoning. No statistical sample size estimation was performed.

The chosen sample size of 50 evaluable patients will, however, be sufficient to reject the null hypothesis of a mean TABR >29 with a power of $>90\%$ if the mean TABR is not greater than 20 BEs per person year with a maximum standard deviation of 15.

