9.2.2 Efficacy Analysis Plan

The analysis of the efficacy of prophylactic treatment with *Wilate* will be based on the FAS and the PP set.

Primarily, all obtained data on treatment characteristics (IMP dosages, frequencies, total consumption) and BEs (duration, frequency, efficacy assessment) will be described by providing summary statistics.

Efficacy of Prophylactic Treatment with Wilate

The efficacy of prophylactic treatment with *Wilate* will be statistically evaluated by comparing the **primary endpoint, i.e., TABR under prophylaxis**, with a predefined threshold of 29 per patient per year. This threshold corresponds to 50% of the TABR reported in GENA-01, a study in which previously treated adolescent and adult patients with severe hemophilia A received on-demand FVIII treatment only.

A confirmative one-sided, one-sample Poisson-test will be used to test whether the mean TABR in patients treated prophylactically with *Wilate* is below the threshold of 29 BEs per patient year ($\alpha = 2.5\%$). A corresponding two-sided 95% CI for the TABR will also be provided.

If μ denotes the mean TABR, then the following pair of hypotheses will be tested:

$$H_0: \mu \geq 29 \text{ vs. } H_1: \mu < 29$$

The null hypothesis will be rejected (at a one-sided alpha level of 2.5%) if the upper limit of the one-sided 97.5% confidence interval for μ is strictly less than 29.

This mentioned confidence interval will be derived from a generalized linear model with a Poisson error, log-link function and $\log(\text{exposure time})$ as offset term.

The **secondary endpoint SABR will be analyzed in complete analogy to the TABR**, the only exception being that, for the comparison of mean SABRs, a predefined threshold of 19.1 per patient per year is chosen; this threshold corresponds to 50% of the SABR reported in GENA-01.

If μ' denotes the mean SABR, then the following pair of hypotheses will be tested:

$$H_0: \mu' \geq 19.1 \text{ vs. } H_1: \mu' < 19.1$$

In addition to the comparison of the patients' ABR to the defined thresholds derived from GENA-01, intra-individual comparisons with each patient's documented pre-study ABR will be performed. For this, descriptive statistics for pre-study and current ABRs and their intra-individual differences will be presented, and the matched-pairs signed rank test ($\alpha = 5\%$) will be used to test for a shift in ABR distributions.

Efficacy in the Treatment of Breakthrough BEs

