5.7.2 Secondary endpoints

All secondary efficacy variables will be analyzed based on the FAS and additionally on the PP population if these populations differ by $>5\%$. In case of surgical endpoints, the analysis will be based on the SURG set (refer to section 5.9) and for PK parameters on the PK set (refer to section 5.8).

Secondary endpoints are:

- Spontaneous annualized bleeding rate (SABR), calculated in analogy with TABR
- Efficacy of *Wilate* in the treatment of breakthrough BEs based on the proportion of BEs successfully treated with *Wilate* (successfully includes efficacy ratings assessed as either 'excellent' or 'good')
- *Wilate* consumption data (FVIII IU/kg per week per subject) for prophylaxis
- Baseline PK parameters for FVIII:C using both the chromogenic (CHR) and one-stage (OS) assays and actual IMP potencies (for details see section 5.8)

STATISTICAL ANALYSIS PLAN

Protocol No: WIL-27

Version Number: 5.0

Date of Issue: 2018-05-08

Page 20 of 27

- Incremental IVR of *Wilate* over time (at baseline, and at 3 and 6 months of treatment)
- Association between ABO blood type and the FVIII:C half-life of *Wilate*
- Association between VWF:Ag concentration and the FVIII:C half-life of *Wilate*
- Safety and tolerability of *Wilate* by monitoring adverse events (AEs) throughout the study (for details see section 5.10.1)
- Immunogenicity of *Wilate* by testing for FVIII inhibitors (for details see section 5.10.3)
- Virus safety in terms of parvovirus B19 (for details see section 5.10.3)

The secondary endpoint SABR will be analyzed in complete analogy to the TABR, the only exception being that, for the comparison of mean SABRs, a predefined threshold of 19.1 per subject per year is chosen; this threshold corresponds to 50% of the SABR reported in GENA-01.

If μ' denotes the mean SABR, then the following pair of hypotheses will be tested:

$$H_0: \mu' \geq 19.1 \text{ vs. } H_1: \mu' < 19.1$$

In addition to the comparison of the subjects' ABR to the defined thresholds derived from GENA-01, intra-individual comparisons with each subject's documented pre-study ABR (based on bleedings documented for at least 6 months prior to study start) will be performed. For this, descriptive statistics for pre-study and current ABRs and their intra-individual differences will be presented, and the matched-pairs signed rank test ($\alpha = 5\%$) will be used to test for a shift in ABR distributions.

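### The primary test and its confidence interval assume pure Poisson variance, while the plan's own mean of 20 and SD of up to 15 allow about 5.6 times that variance

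*SAP*

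**What the plan says.** SAP 5.7.1 names the test: "A confirmative one-sided, one-sample Poisson-test will be used to test whether the mean TABR" lies below 29 bleeding episodes (BEs) per subject-year, at one-sided 2.5%. The null hypothesis is rejected "if the upper limit of the one-sided 97.5% confidence interval for μ is strictly less than 29", and that interval "will be derived from a generalized linear model with a Poisson error, log-link function and log (exposure time) as offset term". The same section adds: "A corresponding two-sided 95% CI for the TABR will also be provided". Protocol 9.2.2 uses the same model.

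SAP 5.7.2 extends the method: "The secondary endpoint SABR will be analyzed in complete analogy to the TABR", with 19.1 as the threshold.

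Protocol 9.1 and SAP 2.5 give the planning figures. Fifty evaluable patients are said to give more than 90% power "if the mean TABR is not greater than 20 BEs per person year with a maximum standard deviation of 15". Each patient is followed for about 6 months.

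Neither document mentions a scale parameter, a sandwich variance, a negative binomial model or a sensitivity analysis for overdispersion.

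**The concern.** A Poisson model with no further term sets each patient's count variance equal to its mean. All patients with the same exposure are then treated as sharing one bleeding rate, with only chance variation around it. The planning SD of 15 is far larger than that model can produce at a mean of 20, so the sample size text and the primary test describe different data.

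The design also points to extra variation:

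- Eligibility (Protocol 4.1.1) sets no limit on prior bleeding rate or prior regimen.
- The prophylactic dose and interval are ranges (Protocol 5.4.2).
- A further bleeding site counts as a separate BE, and a gap in treatment of more than 48 hours splits one BE into two (Protocol 7.2.2), so counts can cluster within a patient.
- For the success rate of BE treatment, the plan itself treats several BEs in one patient as correlated and uses generalized estimating equations. The primary endpoint comes from the same patients and has no such allowance.

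If the variance is understated, the confirmatory error rate is not the one stated, and the intervals reported for TABR and SABR are too narrow.

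**Working it through.** **Inputs.** n = 50 evaluable patients; T = 0.5 year each, so 25 person-years; mean 20 and maximum SD 15 (Protocol 9.1, SAP 2.5); null value 29 and one-sided α = 2.5% (SAP 5.7.1).

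**1. The stated power.** With a difference of 9 and SE = 15/√50 = 2.12:
- normal approximation: Φ(9/2.12 − 1.96) = 98.9%
- one-sample t test: 98.6%
- log scale: Φ(ln(29/20)/(0.75/√50) − 1.96) = 93.9%

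All agree with the claim of more than 90%. All use the SD of 15, so they describe a test that estimates the variance.

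**2. The test actually named.** The exact Poisson test expects 25 × 29 = 725 BEs under the null and rejects at 672 or fewer (size 2.45%). Its power at a mean of 20 is above 99.99%. The SD of 15 plays no part in it.

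**3. Dispersion implied by the plan.** In 6 months the mean count is 20 × 0.5 = 10 and the SD is 15 × 0.5 = 7.5. Then φ = 7.5²/10 = 5.6. A Poisson patient would have an annualized SD of √(20/0.5) = 6.3. At 6.5 months of follow-up, φ is 6.1.

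**4. Standard error and coverage at mean 20, SD 15.** The Poisson SE is √(20/25) = 0.89 and the true SE is 2.12, a ratio of √5.625 = 2.37. Coverage of the nominal 95% interval is 2Φ(1.96/2.37) − 1 = 59% (simulated: 58.8%). At an observed mean of 20 (500 BEs):
- Poisson: 20·exp(±1.96/√500) = 18.3 to 21.8
- scaled: 20·exp(±1.96·√(5.625/500)) = 16.2 to 24.6

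**5. Type I error at mean 29.** The documents give no SD at this mean, so a range of assumptions is shown. Here φ = SD² × 0.5/29, and the error is approximately Φ(−1.96/√φ). The simulations use negative binomial counts, n = 50 and T = 0.5, with 200,000 trials per case (40,000 for SD 10 and 18.1).

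| Assumption at mean 29 | SD | φ | Formula | Poisson limit, simulated | Pearson-scaled limit with t, simulated |
|---|---|---|---|---|---|
| Smaller SD | 10 | 1.7 | 6.8% | 6.6% | 2.5% |
| SD unchanged | 15 | 3.9 | 16.0% | 16.1% | 2.9% |
| φ unchanged | 18.1 | 5.6 | 20.4% | 20.5% | 2.9% |
| Negative binomial dispersion unchanged, (225 − 40)/20² = 0.4625 | 21.1 | 7.7 | 24.0% | 24.5% | 3.1% |
| Coefficient of variation 0.75 unchanged | 21.75 | 8.2 | 24.6% | 25.2% | 3.1% |

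With an SD of 8 at mean 29, φ = 1.10 and the error is about 3.1%.

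**6. After scaling.** At mean 20 and SD 15, power is 94.3% (plain Poisson limit: 99.9%) and coverage is 94.6%. With φ = 5.625, the largest observed mean that still rejects falls from about 26.9 to about 24.0.

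**The case against.** The strongest reply is that 15 is a maximum, offered in a remark on power, and not an estimate. The factor of 5.6 and the 59% coverage are therefore the upper end of what the plan allows. This is right, and the figures should be read that way. But the problem disappears at a mean of 20 only if the SD falls to about 6.3. Even at an SD of 8, φ is 1.6 and coverage is about 88%.

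The plan gives no SD at a mean of 29, so every type I error above rests on an assumption. That also stands, and it is why a range is given.

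At the planning values the decision seldom changes: power is 99.9% with the plain limit and 94.3% with the scaled one, so the two disagree in roughly 5.6% of trials. If the true rate is well below 20 they would almost never disagree. This limits the harm to the decision. It does not help the reported interval, and a prespecified rule should not depend on a favourable result.

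The documents do not name the variance estimator, so a scale factor is not strictly excluded. However, a Poisson error model paired with a one-sample Poisson test is most naturally read, and would most naturally be programmed, without one.

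The planned descriptive statistics would make overdispersion visible, and the signed rank comparison with the pre-study rate does not rely on Poisson variance. Neither replaces the primary interval. The power claim itself is not in error.

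**Conclusion.** The concern holds. As written, the primary analysis uses a variance that the plan's own planning figures exceed by up to 5.6 times, which makes the standard error up to 2.4 times too small.

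- **Interval.** At mean 20 and SD 15, the nominal 95% interval covers about 59%. This rests on the stated maximum SD and 6 months of exposure.
- **Error rate.** At mean 29, one-sided type I error is about 16% to 25% if the SD of 15, the dispersion or the coefficient of variation carries over. It is about 7% with an SD of 10. The stated figure is 2.5%.
- **Decision.** With φ at 5.6, the test result differs only for observed means between about 24.0 and 26.9.
- **SABR.** It inherits the same method. The documents give no planning mean or SD for it, so the size of the effect there cannot be calculated.

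Because this is the confirmatory rule for the primary endpoint, it should be corrected before the analysis.

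**What to change.** Keep the log-link model with log(exposure in years) as offset, and estimate the dispersion instead of fixing it at 1. Choose one method as primary. A suitable specification is a Pearson-scaled Poisson model with φ = Pearson χ²/(n − 1) and limits μ̂·exp(±t(0.975; n − 1)·√(φ/total BEs)). Use its upper 97.5% limit for the decision and its two-sided interval for reporting, for both TABR and SABR.

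A negative binomial model or a Poisson model with patient-level sandwich variance would serve the same purpose. One of them can be a sensitivity analysis, since withdrawals and excluded surgery periods make exposure unequal and the simulations above used equal exposure. Show the plain Poisson result as a sensitivity analysis only.

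State in Protocol 9.1 and SAP 2.5 that the power of more than 90% refers to the dispersion-adjusted test. Align Protocol 9.2.2 with the new wording, or record the change in SAP 3.2, which now says that no deviations are planned.

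The cost is text and one option in the model code. Intervals become wider, and simulated size is 2.5% to 3.1%, slightly above nominal in most cases. No extra patients or data are needed.
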